2.1.4.2.4 Re-emergence time

Timing to consider

In this section, except otherwise specified, the post-dose timing associated to parasitemia will refer to:

- its assigned time point as defined in [Section 2.5.4.1](#), if it exists,
- its actual post-dose timing as defined in [Section 2.5.4.1](#) and expressed in days, if outside defined time windows.

Establishing re-emergence

The re-emergence is defined as the re-appearance of asexual forms of *P. falciparum* irrespective of genotype after clearance of initial infection. Blood thick films performed before Hour 24 (Day 1) time point will not be considered for re-emergence screened.

Time to re-emergence

The time to re-emergence will be the post-dose timing associated to the first positive - observed or imputed - parasitemia after clearance. For patient not reaching parasite clearance of initial infection, the time to re-emergence will be equal to zero.

In patients having reach parasite clearance of initial infection, in case a rescue therapy would be started without previous re-emergence or other species infection, then the time to re-emergence will be the time point of the rescue therapy start. If the case has been classified as a protocol violation, then the time to re-emergence will be censored at the time of the rescue start.

Otherwise, the time to re-emergence will be censored at the post-dose timing associated to the last available patient's thick film before withdrawn (for any reason), or, on/before start of a rescue therapy for other species infection, whichever comes first.

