7.1.2 Noninvestigational Medicinal Products

Rescue therapy will be administered to all participants, either before Day 28 if demanded by the participants health status (see Section 7.7.1 for details), or at Day 28 for participants who reach Day 28 without treatment failure.

Rescue therapy consists of established anti-malarial drug combination per WHO recommendations (6) and per local regulations and the choice of the best therapeutic option is left at investigator's decision.

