7.7.1 Rescue medicine

The study site will supply rescue medication that will be obtained locally upon local recommendation.

The use of established anti-malarial drug combination per WHO recommendations (6) and per local regulations and the choice of the best therapeutic option is left at investigator's decision.

The use of rescue medications is allowed as soon as

- vomiting occurs during FQ dosing or after FQ dosing but before OZ439 administration,
- vomiting occurs within 35 minutes after OZ439 re-dosing (see Section 7.1.1.2), or
- there is evidence of treatment failure (see definition below).

If no rescue medication is administered before Day 28, it will be administered on Day 28.

Treatment failure is defined according to WHO recommendations (2) as follows:

Early treatment failure (one the following)

- danger signs or severe malaria on Day 1, 2, or 3 in the presence of parasitemia;
- parasite count on Day 2 higher than on Day 0, irrespective of axillary temperature;
- parasitemia on Day 3 with axillary temperature ≥ 37.5 °C;
- parasite count on Day $3 \ge 25\%$ on Day 0.

Late clinical failure

- danger signs or severe malaria on any day between Day 4 and Day 28 in the presence of parasitemia, without previously meeting any of the criteria of early treatment failure;
- presence of parasitemia and axillary temperature ≥37.5°C (or history of fever) on any day between Day 4 and Day 28, without previously meeting any of the criteria of early treatment failure.

Late parasitological failure

• presence of parasitemia on any day between Day 7 and Day 28 and axillary temperature <37.5°C, without previously meeting any of the criteria of early treatment failure or late clinical failure.

Before giving a rescue therapy before Day 28, where possible:

- a PK (OZ439 and FQ) sample should be taken
- blood films, parasite genotyping, RT-qPCR, and qPCR must be taken

Following administration of rescue therapy before Day 28, patients should be managed according to local standard of care practices. Safety data, parasitemia (blood films), and PK data should continue to be collected in the e-CRF, according to the study schedule, and up to the end of the study (Day 28) even if re-emergence is confirmed.

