In addition, except where otherwise specified, the following imputation rules will apply in case of missing or out of time window parasite count at a protocol scheduled time point, where the missing count occurs before rescue treatment start, before or on Day 28, or in absence of concomitant fever. In such cases, the missing parasitemia will be considered as:

- positive, if followed or preceded by positive parasitemia,
- negative, if preceded and followed by negative parasitemia,
- missing, if no parasite count available thereafter.

In above bullets:

- positive parasitemia means *P. falciparum* parasite count from thick film ≥ 1 parasite/ μ L, otherwise the parasitemia is negative.
- parasite count from thick film performed after rescue treatment start cannot be used for imputation of missing or out of time window parasite count.

- parasite count from thick film performed the day of rescue treatment start can be used for imputation because this is regarded as before rescue treatment.

In case of concomitant fever related to malaria event (fever is defined in [Section 2.1.4.2.8](#)), a missing parasitemia will be always considered as positive.

In case of missing (or out of time window) parasite count at successive protocol scheduled time points, the above imputations rules could be extended after endorsement of the imputations by the clinical team, otherwise the case will be classified as a deviation preventing evaluation of ACPR as listed in [Section 2.3.2.2](#). Cases of missing body temperature concomitantly with positive parasitemia (observed, or put in place of a missing parasite count as explained above) will be imputed, according to the same principle as for parasitemia imputations, after endorsement of the imputations by the clinical team, or will be classified as deviation.

Efficacy evaluation

Efficacy evaluation will use Early Treatment Failure (ETF), Late Clinical Failure (LCF), Late Parasitological Failure (LPF), and Adequate Clinical and Parasitological Response (ACPR) definitions given below.

Table 1 - Revised WHO classification of treatment failures in areas of intense malaria transmission

Criterion
ETF is defined as one of the following :

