2.3.2 Efficacy populations

2.3.2.1 *Modified Intent-to-treat population*

The modified intent-to-treat (mITT) population includes all randomized patients who received the single administration of IMP, with parasitologically confirmed *P. falciparum* malaria at baseline, having parasitemia data post-randomization.

For analyses and displays, patients will be classified according to the randomized treatment regardless of actual treatment received.

2.3.2.2 *Per-protocol population*

The per-protocol (PP) is the population receiving at least the single administration of FQ 400mg/OZ439, with parasitologically confirmed malaria at baseline, having parasitemia data post-randomization in order to be evaluable for Day 28 ACPR, without major protocol violations possibly affecting efficacy outcome. Note PCR-corrected ACPR applies only to recrudescence i.e. patients with new infections are considered non-evaluable for the analysis of PCR-corrected ACPR see Section 2.1.4).

Parasitemia data for patients with rescue treatment started before the considered time point will be excluded from this time point until Day 28.

In case of vomiting or other reasons interrupting the administration of the complete dose, and if valid parasitemia data post-randomization available, then patients will be included in the PP population.

As defined in [Section 2.1.4.1](#), there are certain criteria that would exclude patients from having an evaluable PCR-corrected ACPR at Day 28:

- Other species infection without *P. falciparum* reemergence,
- Lost to follow-up,
- Withdrawal,
- Protocol violation.

Protocol violations considered above are those potentially impacting efficacy assessments at Day 28:

- Patients who did not take IMP or who needed rescue treatment due to vomiting during IMP administration. Start of vomiting will be classified in 3 categories (< 5 minutes, [5-35] minutes, > 35 minutes and < 6 hours).
- Patient presenting severe malaria or receiving a rescue treatment due to severe malaria during the first 24 hours following IMP start (i.e. wrong inclusion).
- Start of rescue therapy before Day 28 assessment not due to: vomiting during IMP administration, wrong inclusion, treatment failure (per investigator or per WHO criteria), or other species infections.
- Missing baseline parasitemia, and positive parasitemia at 48 or 72 hours.
- Intermittent missing or out of window post-baseline parasitemia preventing to evaluate ACPR Day 28.

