2.4.4.2.7 Time to re-emergence

Incidence of re-emergences will be summarized among patients with complete clearance (i.e those who initially responded). The survival distribution function of the time to re-emergence will be estimated using Kaplan- Meier method. The estimate of the survivor function for each group will be plotted on a same graph. Cumulative number of events (i.e. re-emergence) and censures, in addition to quartiles of the survival times with their 95% confidence interval will be provided by treatment arm. At times $t=$ Day 7, Day 14, Day 21 and Day 28, the number of patients at risk just prior t , the cumulated number of events and censures at t , and the probability that the time to reemergence exceeds t , with its pointwise 95% confidence interval, will be provided.

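### Time to re-emergence: the SAP counts rescue as an event without excepting the systematic Day 28 rescue, so cured completers become Day 28 events

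*SAP*

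**What the plan says.** **The event rule.** SAP 2.1.4.2.4 defines re-emergence as asexual *P. falciparum* appearing again after clearance. It then adds a rule for cleared participants: where "rescue therapy would be started without previous re-emergence or other species infection, then the time to re-emergence will be the time point" of the rescue start. The next sentence takes one group out: "If the case has been classified as a protocol violation, then the time to re-emergence will be censored" at the rescue start. A final clause censors everyone else at the last "thick film before withdrawn (for any reason), or, on/before start of a rescue therapy for other species infection", whichever is first.

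**The systematic rescue.** Protocol 7.7.1 states: "If no rescue medication is administered before Day 28, it will be administered on Day 28". Protocol 7.1.2 confirms that this includes the cured, since rescue is given earlier if health status requires it, "or at Day 28 for participants who reach Day 28 without treatment failure". Footnote c of the schedule of activities also asks for the Day 28 assessments, with rescue, at study discontinuation where possible.

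**The reported quantity.** SAP 2.4.4.2.7 tabulates cumulative events and censorings at Days 7, 14, 21 and 28, and says that "the probability that the time to reemergence exceeds t , with its pointwise 95% confidence interval, will be provided". Protocol Table 8 and the summary table at the end of SAP Appendix B add a Cox model for the time-to-event endpoints. SAP 2.4.4.2.7 itself describes only Kaplan-Meier.

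**The concern.** The event rule depends on a rescue start, and by design every participant still failure-free on Day 28 has one. Nothing in SAP 2.1.4.2.4 separates a rescue that signals suspected failure from one given on schedule to a cured participant. Programmed literally, the rule records cure as re-emergence.

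Time to recrudescence or re-infection is a listed secondary endpoint for the OZ439 dose response (Protocol Section 4, Table 1). At stake are the Day 28 column of its Kaplan-Meier table, its event counts and any Cox model fitted to it. To get a sensible Day 28 figure the programmer would have to depart from the written rule. In an open-label trial that choice should be on paper before the data are analysed.

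**Working it through.** **1. A cured completer taken through the rule.** Take a participant who clears, has negative films through Day 28, and receives the systematic dose that day.
- *Cleared?* Yes.
- *Rescue without previous re-emergence or other species?* Yes. The SAP 2.1.4 rule on same-day films does not help: "parasite count from thick film performed the day of rescue treatment start can be used for imputation because this is regarded as before rescue treatment". A negative Day 28 film therefore counts as before rescue and confirms that nothing had re-emerged.
- *Protocol violation?* No. The violation listed in SAP 2.3.2.2 (repeated in 2.3.5.1) is "Start of rescue therapy before Day 28 assessment not due to: vomiting during IMP administration, wrong inclusion, treatment failure" or other species. A dose given after the Day 28 assessment is outside it.
- *Final censoring clause?* Not reached, because the event rule has already applied. The clause names withdrawal and other-species rescue, not completion.

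Result: an event on Day 28.

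**2. Inputs.** Simulated PCR-corrected ACPR is 72%, 81%, 91% and 97% for OZ439 0, 300, 600 and 1000 mg, with 30 evaluable per arm (SAP 1.3). The plan's enrolment figure reproduces: 30/(1 − 0.15) = 35.3 per arm and 4 × 35.3 = 141.2, against about 35 and 140 stated. The point does not depend on it.

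**3. Counts and Kaplan-Meier at Day 28.** Assume no reinfection, no loss to follow-up, and all true failures before Day 28. Cures = 30 × rate. The estimate is S(28) = S(just before 28) × (1 − events on Day 28 / at risk).

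| OZ439 dose | True failures | Cures at risk on Day 28 | S(28) as written | S(28), systematic rescue censored |
|---|---|---|---|---|
| 0 mg | 8.4 | 21.6 | 0.72 × (1 − 21.6/21.6) = 0 | 0.72 |
| 300 mg | 5.7 | 24.3 | 0 | 0.81 |
| 600 mg | 2.7 | 27.3 | 0 | 0.91 |
| 1000 mg | 0.9 | 29.1 | 0 | 0.97 |
| Total | 17.7 | 102.3 | | |

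Events rise from 17.7 to 120 of 120, and 102.3/120 = 85% of them are cures. The false events all fall on Day 28, so Days 7, 14 and 21 do not change.

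**4. Reinfection.** Re-emergence ignores genotype, and the documents give no crude ACPR, so step 3 is an upper bound. As an illustration, suppose 10% of the cures were reinfected before Day 28. The miscoded number becomes 102.3 × 0.9 = 92.1, and the correct estimates run from 0.72 × 0.9 = 0.65 to 0.97 × 0.9 = 0.87. As written, S(28) is still 0.

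**5. Cox model (illustrative).** 1000 simulated trials had 30 per arm, the same rates, failures spread evenly over Days 10, 14 and 21, dose entered linearly and no other covariate.

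| Coding | Median hazard ratio per 1000 mg (Breslow; Efron ties) | Runs with p < 0.05 |
|---|---|---|
| As written | 0.768; 0.763 | 0.6%; 1.2% |
| Systematic rescue censored | 0.114; 0.108 | 83.8%; 85.5% |

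The dose effect keeps its direction but is heavily attenuated.

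**6. Carry-over.** SAP 2.1.4.2.5 and 2.1.4.2.6 copy events and censorings from time to re-emergence, but censor re-emergence from Day 7 on when PCR is missing. Protocol 9.1.1.4 restricts genotyping to positive films after clearance, so a cured participant has no PCR result. If the Day 28 rescue is treated as a re-emergence with missing PCR, it is censored in both variables. If it is not treated as a parasite re-emergence, the exception does not apply and it stays an event in both.

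**The case against.** The best defence is that the SAP plainly meant unscheduled rescue.
- Its own definition of re-emergence requires parasites, and the rescue sentence is framed as a contingency.
- The ACPR entry in SAP Table 1 lists the reasons for rescue without WHO criteria, and the systematic dose is not among them.
- SAP 2.1.4.2.7 runs time below the LOQ to the end of study when nothing recurs.
- The tables in 2.1.4.1 and 2.1.4.2.1 also have a failure row for rescue without prior failure, with no Day 28 exception, and nobody would read it as turning every ACPR into a failure.
- A 100% event rate on Day 28 would be conspicuous in the output.

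This is good evidence of intent, and it lowers the severity. It does not amend the rule. ACPR is protected because its definition excludes only rescue started earlier and because success has its own row; 2.1.4.2.4 has neither safeguard.

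A reader might also infer more than the documents support:
- *That every rescue start is an event.* Violations and other-species rescue are censored.
- *That the endpoint is inverted.* Only the raw Day 28 event counts run the wrong way. Estimates up to Day 21 are unchanged and the illustrative hazard ratio still favours OZ439.
- *That recrudescence and reinfection are certainly corrupted.* The missing-PCR rule may censor these cases.
- *That 102 miscoded and 18 true failures are expected figures.* They apply PCR-corrected rates to a genotype-blind endpoint.

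**Conclusion.** The concern holds for the Day 28 Kaplan-Meier estimate, the cumulative event count and any Cox analysis of time to re-emergence. As written, the Day 28 estimate is about 0 in all arms; the exception is a cured participant who does not actually receive the systematic dose. The correct values would be at most about 0.72 to 0.97. Up to about 102 of 120 evaluable participants would be miscoded, assuming the planned rates, full follow-up and no reinfection. The Cox figures rest on the further simulation assumptions above and show direction and rough size only.

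Carry-over to recrudescence and reinfection is ambiguous. A reader might take this for a threat to the trial's main conclusion; it is not, because neither ACPR nor the primary exposure-response analysis uses this variable. It should be fixed, as a secondary-endpoint matter.

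**What to change.** Change the analysis text only; rescue practice is untouched.

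1. In SAP 2.1.4.2.4, limit the rule that rescue counts as an event to unscheduled rescue started before the Day 28 assessment.
2. Add a sentence such as: *Participants without re-emergence whose only rescue is the systematic Day 28 dose, or the same dose given at study discontinuation, are censored at their last available thick film.* The discontinuation dose needs naming because its route is unclear: it could be an event, a violation or a withdrawal, and it could fall before Day 28.
3. Cross-refer to this sentence in 2.1.4.2.5 and 2.1.4.2.6, which also removes the missing-PCR ambiguity for cured participants.

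The cost is two sentences and two cross-references, with no new data. It should be done before the time-to-event programs are written.

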2.1.4.2.5 Time to recrudescence

The time to recrudescence will be equal to the time to re-emergence (failures or censures), except in case of *P. falciparum* re-emergence on or after Day 7 where the following rule will apply:

- re-emergence is due to: "Falciparum reinfection" or "Other species with falciparum reinfection". Then the time to recrudescence will be censored from the day of reinfection.
- re-emergence is undetermined, negative or missing PCR. Then the time to recrudescence will be censored from the day of re-emergence.

2.1.4.2.6 Time to reinfection

The time to reinfection will be equal to the time to re-emergence (failures or censures), except in case of *P. falciparum* re-emergence on or after Day 7 where the following rule will apply:

- re-emergence is due to: “*P. falciparum* recrudescence” or “Other species with *falciparum* recrudescence”. Then the time to reinfection will be censored from the day of recrudescence.
- re-emergence is undetermined, negative or missing PCR. Then the time to reinfection will be censored from the day of re-emergence.

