9.1.1.4 Quantitative PCR, parasite genotyping analysis

Blood samples to measure parasitemia by qPCR will be taken according to SoA; qPCR analysis will be performed by the testing laboratory at all scheduled time points.

Blood samplings for genotyping will be collected according to SoA and at the time-points when recrudescence or re-infection after initial parasite clearance was shown on the blood slide. Parasite genotyping analysis will be performed by the testing laboratory on previously collected blood spot sample only in case of a positive blood film after initial parasite clearance: one pre-dose sample and one sample at 18 or 24 hours post dosing. A further sample will be analyzed at the time point at which recrudescence/re-infection occurs.

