10.3.1.1 Definition of ACPR, recrudescence, and re-infection

ACPR is defined based on WHO recommendations (2) as follows:

ACPR

• absence of parasitemia (blood films) on Day 28, irrespective of axillary temperature, without previously meeting any of the criteria of early treatment failure or late clinical failure or late parasitological failure (see definitions in Section 7.7.1) or having received a rescue treatment for malaria in the conditions defined in Section 7.7.1.

Recrudescence

• appearance of asexual parasites after clearance of initial infection with a genotype identical to that of parasites present at baseline.

Re-infection

• appearance of asexual parasites after clearance of initial infection with a genotype that differs from that of parasites present at baseline. Confirmed new infection will not be regarded as treatment failure or recrudescence.

Crude ACPR

• Crude ACPR applies to both recrudescence of the parasite clone responsible for baseline infection and re-infection by a different clone.

PCR-corrected ACPR

• the PCR-corrected ACPR applies only to recrudescence (re-emergence of the original clone of parasite that is present at baseline). Recrudescence is distinguished from reinfection by genotyping the parasite clone.

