Recrudescence: The appearance of asexual parasites after clearance of initial infection with a genotype identical to that of parasites present at baseline. Recrudescence is confirmed by microscopy (positive blood smear) and by genotyping PCR analysis.

Re-infection: The appearance of asexual parasites after clearance of initial infection with a genotype that differs from that of parasites present at baseline. Re-infection is confirmed by microscopy (positive blood smear) and by genotyping PCR analysis.

Treatment failure: Any patients who met any of the criteria for ETF, LCF or LPF.

Crude ACPR does not distinguish between re-infection (by a new clone of parasite) and recrudescence (re-emergence of the original clone of parasite that was present at baseline); i.e. presence of either a new clone or genotypically identical parasite will be considered a treatment failure.

PCR-corrected ACPR applies only to recrudescence; (i.e. patients with re-infection are considered non-evaluable for the analysis of PCR-adjusted ACPR). Presence of a genotypically identical parasite will be considered a treatment failure.

Genotyping adjustment

LCF occurring from Day 7 or LPF will be sub-classified as follows using parasite genotyping results:

- *P. falciparum* recrudescence, if no other species reported in eCRF and genotyping result is “recrudescence”
- *P. falciparum* reinfection, if no other species reported in eCRF and genotyping result is “reinfection”

- Other species with *P. falciparum* recrudescence, if other species reported in eCRF and genotyping result is “recrudescence”
- Other species with *P. falciparum* reinfection, if other species reported in eCRF and genotyping result is “reinfection”
- Undetermined, negative or missing PCR, if genotyping result is “Undetermined”, “negative”, “undetermined” or “missing”, with or without other species infection.

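### Time to reinfection (SAP 2.1.4.2.6) counts every re-emergence before Day 7, and some rescue starts, as reinfection events, against the SAP's own definition

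*SAP*

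**What the plan says.** **Reinfection rule (SAP 2.1.4.2.6).** "The time to reinfection will be equal to the time to re-emergence (failures or censures), except in case of". What follows limits the exception to P. falciparum re-emergence from Day 7. There, cases typed as recrudescence, and cases whose PCR is undetermined, negative or missing, are censored.

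**Re-emergence rule (SAP 2.1.4.2.4).** Any return of asexual P. falciparum after clearance counts, whatever its genotype. The first positive film may be observed or imputed, and films count from Hour 24. For a cleared patient who starts rescue with no earlier re-emergence or other-species infection, "then the time to re-emergence will be the time point of the rescue therapy start". The exception reads: "If the case has been classified as a protocol violation, then the time to re-emergence will be censored". A further sentence reads: "For patient not reaching parasite clearance of initial infection, the time to re-emergence will be equal to zero".

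**Definitions.** Protocol 10.3.1.1 defines re-infection as "appearance of asexual parasites after clearance of initial infection with a genotype that differs from that of parasites present at baseline". SAP 2.1.4 repeats this and adds: "Re-infection is confirmed by microscopy (positive blood smear) and by genotyping PCR analysis". Neither definition has a Day 7 limit.

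**Use of genotype.** SAP 2.1.4 limits its classes by time: "LCF occurring from Day 7 or LPF will be sub-classified as follows using parasite genotyping results". The genotyping trigger in Protocol 9.1.1.4 has no such limit; the analysis is done "only in case of a positive blood film after initial parasite clearance".

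**The concern.** The rule for time to recrudescence (2.1.4.2.5) has the same default and the same Day 7 limit. There the default makes sense: an early return of parasites is taken to be the original infection, which agrees with 2.1.4.1, where a late clinical failure before Day 7 is a treatment failure. In 2.1.4.2.6 the labels are swapped but the default is kept, so the same early return is also taken to be a new infection.

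One case then appears as an event in both curves, and failures of the original infection are reported as new infections in the reinfection incidence and Kaplan-Meier output. A rescue start with no positive film can enter the same way, although it cannot meet a definition that requires a positive smear and a PCR result.

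**Working it through.** No figure in the plan feeds this rule, so there is none to reproduce. The check is to pass each type of case through SAP 2.1.4.2.4 to 2.1.4.2.6 as written and compare the result with the definition in 2.1.4. Days 5 and 14 are examples from either side of the Day 7 limit.

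| Case | Time to recrudescence | Time to reinfection | Reinfection by the 2.1.4 definition? |
|---|---|---|---|
| Re-emergence Day 5, recrudescent | event | event | no |
| Re-emergence Day 5, PCR undetermined or missing | event | event | not confirmed |
| Re-emergence Day 5, different genotype | event | event | yes |
| Re-emergence Day 14, recrudescent | event | censored | no |
| Re-emergence Day 14, PCR undetermined or missing | censored | censored | not confirmed |
| Re-emergence Day 14, different genotype | censored | event | yes |
| Rescue Day 5, no re-emergence, not a violation | event | event | no |
| Rescue Day 14, no re-emergence, not a violation | event by default | event by default, or censored if the missing-PCR bullet is read to cover it | no |
| Rescue Day 5, protocol violation | censored | censored | no |
| Never cleared | time zero | time zero | no |

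From Day 7 the two endpoints separate re-emergences cleanly. Before Day 7 every re-emergence is an event in both. An imputed positive is in the same position and has no film to genotype: SAP 2.1.4 treats a missing count as positive when there is concomitant malaria-related fever.

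The rescue route has a different source. It comes from 2.1.4.2.4 and has no Day 7 limit. It is narrowed by SAP 2.1.4 (Table 1) and 2.3.2.2, which class rescue for vomiting during dosing, for severe malaria in the first 24 hours, or for reasons other than failure as deviations, and these are censored. What remains appears to be mainly failure judged by the investigator without a positive film. That is an inference; the documents give no count.

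**Illustration only.** Assume 120 patients (the planned evaluable number, SAP 1.1), all cleared. Let e be early re-emergences and q rescue-only cases, all at Day 5 and none a true reinfection. Assume also 10 late recrudescences censored at Day 14 and 6 true reinfections at Day 21. The number at risk at Day 21 is n = 120 − e − q − 10. The Day 28 cumulative incidence is 1 − (1 − (e+q)/120)(1 − 6/n) as written, and 6/n with the early cases censored.

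| e, q | n | As written | Early cases censored |
|---|---|---|---|
| 0, 0 | 110 | 5.5% | 5.5% |
| 1, 0 | 109 | 6.3% | 5.5% |
| 2, 1 | 107 | 8.0% | 5.6% |
| 4, 2 | 104 | 10.5% | 5.8% |
| 6, 3 | 101 | 13.0% | 5.9% |

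Apart from n = 120, every count here is assumed. The table shows the direction of the error and how it grows, not its size in this trial.

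**The case against.** The plan uses genotype only from Day 7 in three places: the sub-classification in 2.1.4, the endpoint table in 2.1.4.1 and the recrudescence rule in 2.1.4.2.5. A Day 7 threshold is thus a consistent convention, and early re-emergence after confirmed clearance may be rare. The protocol's endpoint is the composite of recrudescence or re-infection; a separate time to reinfection appears only in the SAP. SAP 2.4.4.2.9 gives it the Kaplan-Meier summaries of 2.4.4.2.7, with no test between arms. The closing summary table does name a Cox model on a row that includes recrudescence or re-infection, but the body text specifies none for this endpoint.

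All of this stands as to weight, and the first point shapes the remedy. It does not rescue the rule: if early re-emergence is by convention the original infection, it should not be an event in the reinfection curve.

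A reader might go further in four ways that the documents do not support.

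- **Reach measured by film times or genotype classes.** Scheduled films before Day 7 are opportunities, not events, and re-emergence first requires clearance. The genotype classes in 2.1.4 are defined only for late clinical failure from Day 7 and late parasitological failure, so counting them before Day 7 measures nothing.
- **A spurious dose trend.** The planning success rates of 72%, 81%, 91% and 97% imply Day 28 failure of 28%, 19%, 9% and 3%. They say nothing about failure before Day 7.
- **An error in time to recrudescence as well.** Its early default agrees with 2.1.4.1.
- **Almost every responder becoming an event through the Day 28 rescue.** Protocol 7.7.1 gives rescue at Day 28 to everyone not yet rescued, and 2.1.4.2.4 does not exclude it. Taken literally, that is about 30 × (0.72 + 0.81 + 0.91 + 0.97) = 102 of 120 patients at the planning rates. Nothing suggests that this is meant; it calls for one clarifying sentence.

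**Conclusion.** The point holds as an error in a stated derivation. Before Day 7 the reinfection rule has no genotype condition, contradicts the definition in SAP 2.1.4 and Protocol 10.3.1.1, and makes one case an event in two curves that should exclude each other. No other section corrects it. The rescue route is a second, separate fault inherited from 2.1.4.2.4; from Day 7 its handling is unclear rather than plainly wrong.

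The size cannot be derived, because the documents give no rate of early re-emergence or of rescue without re-emergence. If there are no such cases, the output does not change. The consequence is confined to a secondary endpoint. The primary exposure-response analysis, crude ACPR and time to re-emergence do not use the 2.1.4.2.6 rule. It should be corrected, but it does not threaten the trial's main conclusion.

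**What to change.** In SAP 2.1.4.2.6:

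- **(a) Before Day 7.** Censor any re-emergence, observed or imputed, at its time. From Day 7 keep the existing rule, so that only genotype-confirmed reinfection is an event. This follows the SAP's own use of genotype from Day 7. The price is that a true reinfection before Day 7 is censored here and stays an event in 2.1.4.2.5. If the sponsor prefers to use the early genotype available under Protocol 9.1.1.4, a confirmed early reinfection must also be censored in 2.1.4.2.5, so that no case is an event in both curves.
- **(b) Rescue without re-emergence.** Censor at the rescue start, at any time. This also settles whether the missing-PCR bullet applies from Day 7.
- **(c) Two statements.** Say that never-cleared patients, who carry time zero, are not reinfection events; 2.4.4.2.7 restricts only its incidence summary to cleared patients and says nothing of the kind for the curves. Say also that the systematic Day 28 rescue is not an event.

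The cost is a few sentences and a change to the derivation program. No new data are needed.
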